2. OBJECTIVES

The objectives of this study are as follows:

Primary Objective:

- To determine the effect of SCD-044 treatment on moderate to severe plaque psoriasis, as measured by proportion of subjects showing at least 75% improvement in Psoriasis Area and Severity Index (PASI) at week 16.

Secondary Objectives:

- To evaluate the efficacy of SCD-044 as measured by proportion of subjects achieving predefined improvement in Investigator's Global Assessment (IGA) of disease severity
- To evaluate the efficacy of SCD-044 as measured by proportion of subjects achieving predefined improvement in Psoriasis Area and Severity Index (PASI) and change in PASI scores over the treatment period
- To assess the effect of SCD-044 on the subject reported outcome measure of Psoriasis Symptoms

and Signs Diary (PSSD)

- To assess the effect of SCD-044 on quality of life, as measured by Dermatology Life Quality Index (DLQI)
- To evaluate the efficacy of SCD-044 as measured by change in body surface area (BSA) involvement over the treatment period
- To assess the effect of SCD-044 on Patient Global Impression of Severity (PGIS)
- To assess the effect of SCD-044 on Patient Global Impression of Change (PGIC)
- To evaluate the PASI75 response in non-responders at low dose and intermediate dose when switched to high dose of SCD-044
- To assess the safety and tolerability of SCD-044 in subjects with moderate to severe plaque psoriasis
- To characterize the pharmacokinetics (PK) of SCD-044 in subjects with moderate to severe plaque psoriasis

Tertiary Objectives:

- To evaluate the efficacy of SCD-044 in the treatment of Scalp psoriasis as measured by Scalp IGA
- To evaluate the efficacy of SCD-044 in the treatment of nail psoriasis as measured by modified Nail Psoriasis Severity Index (mNAPSI) scores
- To evaluate the efficacy of SCD-044 in the treatment of psoriatic arthritis as measured by American College of Rheumatology (ACR) response
- To evaluate the efficacy of SCD-044 in the treatment of Palmoplantar Psoriasis as measured by Palmoplantar Physician Global Assessment (PPPGA) score

Exploratory Objectives:

- To examine the pharmacodynamic/pharmacokinetic (PK/PD) relationship between SCD-044 plasma concentrations and PASI response
- To examine the PK/PD relationship between SCD-044 plasma concentrations and [REDACTED] parameters [REDACTED]
- [REDACTED]
- [REDACTED]
- To evaluate the effect of SCD-044 on subject reported outcome of itching associated with Psoriasis

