#### 4.3 Other secondary endpoints

The other (non-key) secondary endpoints of this study are:

- [REDACTED]
- [REDACTED]
- [REDACTED]
- Change from Baseline in PSSD score at Weeks 16, [REDACTED] and 52
- Change from Baseline in DLQI score at Weeks 16, [REDACTED] and 52
- Proportion of subjects with DLQI score of 0 or 1 at Weeks [REDACTED] 52.
- Proportion of subjects with IGA score of “clear” or “almost clear” with at least two-grade [REDACTED]
- [REDACTED]
- [REDACTED]
- Change from baseline in BSA involvement at Weeks [REDACTED] and 52
- Change from baseline in PGIS at Weeks [REDACTED] and 52
- Proportion of subjects with improvement in PGIC at Weeks [REDACTED] 52
- [REDACTED]
- Proportion of non-responders (<PASI75) at Week 16 in the low and intermediate dose groups who achieve a PASI75 response at Week [REDACTED] Week 52 after switch over to high dose
- [REDACTED]
- [REDACTED]
- Frequency, type, and severity of adverse events (AEs)

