#### 4.4 Tertiary endpoints

Tertiary endpoints of this study are:

- Proportion of subjects with Scalp IGA “clear” or “almost clear” with at least two-grade reduction from baseline at Weeks [REDACTED] and 52 among subjects with a baseline Scalp IGA score of  $\geq 3$
- Proportion of subjects with nail psoriasis (baseline mNAPSI score of  $\geq 20$ ) who achieve at least a 75% improvement from baseline in total fingernail mNAPSI at Weeks [REDACTED] and 52
- Proportion of psoriatic arthritis subjects who achieve ACR20 response at Weeks [REDACTED] and 52
- Proportion of subjects with PPPGA score of 0 or 1 at Weeks [REDACTED] and 52 among subjects with a baseline PPPGA score of  $\geq 3$

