#### 4.5 Exploratory endpoints

Exploratory endpoints include:

- [REDACTED]
- [REDACTED]
- [REDACTED]
- Proportion of subjects achieving  $\geq$  4-point improvement in Itch Numeric Rating Scale (NRS) from baseline at Weeks [REDACTED], and 52 among subjects with a baseline Itch NRS of  $\geq$  4
- Proportion of subjects achieving  $\geq$  4-point improvement in Scalp Itch NRS from baseline at Weeks [REDACTED] and 52 among subjects with a baseline Scalp Itch NRS of  $\geq$  4
- Change from baseline in subject global assessment of PtA-P at Weeks [REDACTED] and 52 among subjects with PsA at baseline
- [REDACTED]

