- Part II Baseline is defined as the last assessment, scheduled or not, prior to the first dose of the study drug in Part II. Part II baseline will be used in analysis of findings collected in Parts II, III and IV for subjects who were re-randomized in Part II to another treatment (i.e. SCD-044 [ ] or [ ] after being treated with Placebo in Part I or to SCD-044 [ ] after being treated with SCD-044 [ ] or [ ] in Part I). Throughout this SAP, if the word “baseline” is used without qualification “Part I” or “Part II”, it will refer to Part I baseline.

In by-visit summaries, only data collected on scheduled visits/timepoints will be summarized. Data from unscheduled assessments will be included in listings and may be used in determination of baseline if applicable.

Relative days will be calculated relative to date of first dose of the study drug. Relative days will be calculated as follows only when the full assessment date is known (i.e., partial dates will have missing relative days).

For assessment on or after the day of first dose of the study drug:

Relative Day = Date of Assessment – Date of First Dose of Study Drug+1.

For assessment before the day of first dose of the study drug:

Relative Day = Date of Assessment – Date of First Dose of Study Drug.

All dates will be displayed in DDMMYY format.

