### **6.1.1 Treatment Groups**

Data collected up to Week 16 visit will be analyzed by treatment groups based on the subject’s treatment in Part I of the study:

- Placebo

- SCD-044 [REDACTED]
- SCD-044 [REDACTED]
- SCD-044 [REDACTED]

Efficacy data collected after Week 16 visit (i.e., Parts II-IV), as well as disposition and compliance in Parts II-IV, will be analyzed by treatment groups based on the responder status at the end of Part I (Week 16) (i.e.,  $\geq$  PASI50 or  $<$  PASI50), the subject's treatment in Part I and the subject's treatment in Part II of the study:

- Part I Responders
  - Placebo/SCD-044 [REDACTED]
  - Placebo/SCD-044 [REDACTED]
  - SCD-044 [REDACTED]
  - SCD-044 [REDACTED]
  - SCD-044 [REDACTED]
- Part I Non-Responders
  - Placebo/SCD-044 [REDACTED]
  - Placebo/SCD-044 [REDACTED]
  - SCD-044 [REDACTED]
  - SCD-044 [REDACTED]

Safety data collected after Week 16 visit (i.e., Parts II-IV) will be analyzed by treatment groups based on the subject's treatments in Part I and in Part II:

- Placebo/SCD-044 [REDACTED]
- Placebo/SCD-044 [REDACTED]
- SCD-044 [REDACTED]

Adverse events and concomitant medications will be additionally analyzed for the entire study. Details are provided in the sections 6.11.1 and 6.11.6.

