#### **6.8.3.2 Binary endpoints**

Binary endpoints include:

- PASI50, PASI75, PASI90, PASI100 responses (i.e. reduction of at least 50%, 75%, 90% and 100% from baseline in PASI)
- IGA response (achieving IGA score of “clear” or “almost clear” with at least two-grade reduction from baseline)
- achieving PGIC improvement,
- Scalp IGA response (achieving Scalp IGA score of “clear” or “almost clear” with at least two-grade reduction from baseline).
- mNAPSI response (achieving at least a 75% improvement from baseline in total fingernail mNAPSI)
- ACR20 response (see the definition in the next section)
- achieving PPPGA score of 0 or 1
- achieving DLQI scores of 0 or 1
- achieving  $\geq$  4-point improvement in Itch NRS from baseline
- achieving  $\geq$  4-point improvement in Scalp Itch NRS from baseline.

Note that for all binary endpoints above that involve change from baseline or percent change from baseline, Part II baseline will be used for the groups that switch treatment in Part II, while Part I baseline will be used for the groups that stay on the same treatment throughout the study.

Number and percentage of subjects achieving these endpoints will be presented by treatment group along with 95% confidence interval for percentages based on binomial proportion.

Additionally shift tables will be created for IGA presenting shifts from baseline to post-baseline visits in Part I and Part II separately.

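### The switch-to-high-dose PASI75 endpoint selects non-responders from Week 0 but scores them from Week 16, and the overall time-to-response curves keep only subjects who never switched

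*SAP*

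**What the plan says.** **Endpoint.** Protocol section 2 lists as a secondary objective: "To evaluate the PASI75 response in non-responders at low dose and intermediate dose when switched to high dose of SCD-044". SAP 4.3 turns this into an endpoint: "Proportion of non-responders (<PASI75) at Week 16 in the low and intermediate dose groups who achieve a PASI75 response at Week", with later time points (partly redacted, Week 52 visible) after the move to high dose.

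**Baseline.** SAP 6.1 gives a default: where baseline is unqualified, "it will refer to Part I baseline". It also says "Part II baseline will be used in analysis of findings collected in Parts II, III and IV" for subjects moved to another treatment in Part II, and its list includes subjects who change from one SCD-044 dose to another. SAP 6.8.3.2 repeats the rule for responder endpoints, PASI75 among them: "Part II baseline will be used for the groups that switch treatment in Part II". Part II baseline is the last value before the first Part II dose, normally Week 16.

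**Grouping.** SAP 6.1.1 forms the post-Week-16 efficacy groups on Part I response, with the cut at PASI50 rather than PASI75.

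**Time to response.** SAP 6.8.3.5 plans three analyses: Part I by initial arm; Parts II and III in re-randomised subjects, scored from Part II baseline; and the whole study, limited to active-arm subjects who never changed treatment. Protocol section 3 makes the move from low or intermediate to high dose depend on Week 16 PASI response, with the cut-off redacted.

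**Subset endpoints.** SAP 4.5 restricts the itch endpoint ("and 52 among subjects with a baseline Itch NRS of" 4 or more, and likewise for scalp itch). SAP 4.4 restricts Scalp IGA ("and 52 among subjects with a baseline Scalp IGA score of" 3 or more).

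**The concern.** The switch-to-high endpoint uses one scale to call a subject a non-responder and another to decide whether that subject later responds. A reader of the reported percentage will take it as the share of failures rescued to PASI75 in the usual sense. It is not that share, and the improvement from Week 0 that it demands varies from subject to subject.

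The overall curves have a different problem. Membership is decided by something that happens after randomisation and depends on the outcome: a low- or intermediate-dose subject who does poorly at Week 16 is switched and leaves the curve from first dose onward. No visible text gives a high-dose subject anywhere to switch to, so high-dose non-responders stay in theirs. In a dose-ranging study, that tilts a descriptive comparison of onset across doses towards the lower doses.

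The Parts II/III IGA analysis has a smaller defect: a switcher who is at IGA 0 or 1 at Week 16 cannot fall two grades, so that subject is counted at risk with no possible event.

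**Working it through.** The documents give no rate or sample size for these outputs, so there is no planned figure to reproduce.

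**1. The PASI75 bar.** Let r be improvement from Week 0 at Week 16. The Week 16 score is (1 - r) of the Week 0 score. PASI75 from Week 16 needs a score of at most 0.25(1 - r) of the Week 0 score, so the required improvement from Week 0 is 1 - 0.25(1 - r).

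| r at Week 16 | Required improvement from Week 0 |
|---|---|
| -20% | 70% |
| 0 | 75% |
| 20% | 80% |
| 40% | 85% |
| 49% | 87.25% |
| 50% (limit if switchers are below PASI50) | 87.5% |

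Two paths show both directions:
- PASI 20, then 10.2, then 4: 1 - 4/20 = 80% from Week 0, but 1 - 4/10.2 = 60.8% from Week 16. Not counted.
- PASI 20, then 24, then 6: 1 - 6/20 = 70% from Week 0, but 1 - 6/24 = 75% from Week 16. Counted.

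**2. Who is in the denominator.** A low- or intermediate-dose subject between PASI50 and PASI75 at Week 16 is a non-responder under SAP 4.3 but a Part I responder under SAP 6.1.1. If such subjects stay on their dose, the text does not settle whether they count in the endpoint. SAP 6.1.1 has four non-responder columns, two of them from placebo. That layout fits a switch below PASI50, but the rule itself is redacted.

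**3. Selection in the overall curves.** Take 60 per arm (240 at 1:1:1:1, Protocol 4.1). Assume that stayers are those at PASI50 or better, with assumed Week 16 rates P50 and P75, and that a fraction d leaves before Week 16 without response. Early leavers also never switched, so they are kept.

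- Share kept = d + (1 - d) x P50
- PASI75 by Week 16 among those kept = (1 - d) x P75 / share kept
- PASI75 by Week 16 among all randomised = (1 - d) x P75

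| P50, P75 (assumed) | d = 0: kept vs all | d = 10%: kept vs all |
|---|---|---|
| 30%, 10% | 33% vs 10% | 24% vs 9% |
| 40%, 20% | 50% vs 20% | 39% vs 18% |
| 50%, 30% | 60% vs 30% | 49% vs 27% |
| 60%, 40% | 67% vs 40% | 56% vs 36% |

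For the second row with d = 0: 24 of 60 are kept and 12/24 = 50%, against 12/60 = 20%. These are crude proportions. In a Kaplan-Meier curve early leavers are censored, so how far they dilute the effect also depends on when they leave.

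**4. IGA risk set.** Response needs grade 0 or 1 after a fall of at least two grades. From grade 1 the largest possible fall is one; from grade 0 it is none. SAP 6.1.1 has placebo switch columns under Part I responders, so such subjects can exist. Their number cannot be derived.

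**5. Subset endpoints.** If eligibility follows the Week 0 default while response is scored from Week 16, switchers with Week 16 itch of 0-3, or Scalp IGA of 0-1, are counted but cannot respond. If Part II baseline governs both, they leave the denominator. The text allows either reading.

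**The case against.** **Re-baselining is deliberate.** The SAP applies it consistently to switchers. It isolates change after the new dose, and against its own baseline the bar is a constant 75%. A Week 0 rate credits improvement already gained in Part I. This stands: the Week 16 rate is legitimate, and which rate leads is a preference. The Part I credit is limited if switchers are below PASI50, because reaching PASI75 from Week 0 then needs a further fall of 1 - 0.25/(1 - r), which exceeds 50% whenever an improver's r is below 50%.

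**That SAP 6.8.3.2 governs this endpoint is partly inference.** SAP 4.3 names no baseline, and some protocol endpoint bullets are redacted. But PASI75 is in the list that the rule covers, no exception is made, and SAP 6.1 names dose-to-dose switchers. If another baseline is meant, the SAP should say so.

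**The overall analysis states its restriction openly**, plans no between-arm test and sits beside an unselected Part I analysis. All true. Disclosure limits the harm but does not remove the selection.

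**Stronger readings that the documents do not support.** A reader might put the bar as high as 93.75%; that requires switching up to PASI75, whereas the SAP 6.1.1 columns fit a PASI50 cut. A reader might take 50% versus 20% as an estimate of bias; it rests wholly on assumed rates. A reader might conclude that itch and scalp switchers are bound to fail; that holds under only one of two permitted readings. A reader might see a conflict with the Week 28 PASI rule in Protocol 7.1.9; that rule names no baseline, so no contradiction is shown.

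**Conclusion.** The point holds with limited scope.

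- **Switch-to-high endpoint.** Reported from Week 16 alone, it does not show how many non-responders reach PASI75 on the scale that classified them. The algebra is exact. The upper limit of just under 87.5% assumes a PASI50 switch cut. The effect on the reported rate is unknown.
- **Overall time to response.** The low- and intermediate-dose curves are selected on Week 16 response, in a direction that favours those doses. The size is unknown because the switch rule and response rates are not given, and early dropouts dilute it.
- **Parts II/III time to IGA response.** The risk set contains subjects who cannot have the event; their number is unknown.

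It would be wrong to infer that the trial's main conclusions are at risk. SAP 6.1.2 draws no inference from these other endpoints. The Week 16 primary and key secondary analyses, the MMRM (data to Week 16 only) and the Part I time-to-response analysis are untouched. IGA shift and category tables will still show status after the switch. The reason to act is that a named secondary objective would otherwise lack a clearly interpretable rate, and the remedy is cheap.

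**What to change.** 1. Report the SAP 4.3 switch-to-high PASI75 endpoint from Week 0 and from Week 16, each labelled, with a note that the Week 0 rate includes Part I improvement.
2. Reconcile the PASI75 definition of non-response in SAP 4.3 with the PASI50 grouping in SAP 6.1.1, and state which subjects form the denominator.
3. Either drop the overall time-to-response curves and rely on Part I, or include all subjects randomised to SCD-044 by initial arm, with the switch as a competing event. Simple censoring at the switch is not equivalent, because switching depends on response.
4. Exclude switchers at IGA 0-1 at Week 16 from the Parts II/III IGA risk set and report how many there are.
5. For itch, scalp itch and Scalp IGA, name one baseline and use it for both eligibility and response.

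**Cost:** SAP wording, one added set of columns for switchers and, if the overall curves are kept, a cumulative-incidence table. Week 0 and Week 16 values are already collected. The main downside is two rates for one endpoint, so the labels must be clear.

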4. STUDY POPULATION

4.1 Number of Subjects

Approximately 240 subjects will be enrolled in the study in a 1:1:1:1 ratio to the following treatment groups: [REDACTED]

[REDACTED]

[REDACTED]

[REDACTED]

[REDACTED]

[REDACTED]

The number of subjects contributed by a site will not exceed approximately [REDACTED] of total study population unless approved by the Sponsor. Enrolment in a country other than USA will be limited to approximately [REDACTED] unless approved by the Sponsor.

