- Level of lymphocyte sub-types and cytokines in blood/plasma/serum.

Other exploratory analyses may be performed based on available data. The Intent-to-Treat Population (ITT) will be used for all efficacy analyses.

Efficacy Analysis

The primary and key secondary efficacy variables will be analyzed using a Cochran-Mantel-Haenszel (CMH) test, stratified by gender and prior biologic therapy (Yes/No), and using the Intent-to-Treat (ITT) Population. Additional details will be included in the SAP

Tests for superiority over placebo for the primary and the key secondary endpoint will be conducted using a hierarchical closed testing step-down approach to preserve the overall Type I error rate of 0.05.

[REDACTED]

[REDACTED]

[REDACTED]

Sensitivity Analyses

For sensitivity testing, the primary and key secondary endpoints analyses will also be performed using the per protocol (PP) population.

Additional sensitivity analyses will be performed for the primary efficacy variable using the following populations:

- The Intent-to-Treat (ITT) Population using Last-Observation-Carried-Forward imputation (LOCF)
- The Per Protocol (PP) Population, using Observed Cases (OC)
- The Intent-to-Treat (ITT) Population, active treatment worst case (ATWC), defined as all missing assessments in the placebo group defaulted to responder but missing assessments in active treatment arm defaulted to nonresponder. Full tipping point analysis methods will be discussed in the SAP.

Subgroup analysis on the stratification factors gender and prior biologic therapy (yes/no) may be performed for the primary and key secondary endpoints.

Tests for superiority over placebo for the primary and the key secondary endpoint will be conducted using a hierarchical closed testing step-down approach to preserve the overall Type I error rate of 0.05.

Continuous secondary efficacy endpoints will be analyzed using a mixed model repeated measures procedure (MMRM) based on the ITT Population. The MMRM will include fixed effects for treatment, visit, treatment by visit interaction, gender, prior biologic therapy (yes/no), and Baseline value as a covariate. This MMRM approach will also be applied at the single time point of Week 16. All such analyses are considered supportive. Additional details of the statistical approach will be provided in the statistical analysis plan.

Further details will be provided in the Statistical Analysis Plan (SAP).

[REDACTED]

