### 2.3 Secondary Objectives

The secondary objectives of this study are:

- To evaluate the efficacy of SCD-044 as measured by proportion of subjects achieving predefined improvement in Investigator's Global Assessment (IGA) of disease severity

- To evaluate the efficacy of SCD-044 as measured by proportion of subjects achieving predefined improvement in Psoriasis Area and Severity Index (PASI) and change in PASI scores over the treatment period
- To assess the effect of SCD-044 on the subject reported outcome measure of Psoriasis Symptoms and Signs Diary (PSSD)
- To assess the effect of SCD-044 on quality of life, as measured by Dermatology Life Quality Index (DLQI)
- To evaluate the efficacy of SCD-044 as measured by change in body surface area (BSA) involvement over the treatment period
- To assess the effect of SCD-044 on Patient Global Impression of Severity (PGIS)
- To assess the effect of SCD-044 on Patient Global Impression of Change (PGIC)
- To evaluate the PASI75 response in non-responders at low dose and intermediate dose when switched to high dose of SCD-044
- To assess the safety and tolerability of SCD-044 in subjects with moderate to severe plaque psoriasis
- [REDACTED]

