## 6. STATISTICAL METHODS OF ANALYSIS

### 6.1 General Principles

The statistical analyses will be performed using SAS® Version 9.4 (or higher). All tables, figures and listings will be produced in landscape format.

In general, all data will be listed by subject and visit/time point where appropriate. The summary tables will be stratified by, or have columns corresponding to, treatment groups (see section 6.1.1).

The total number of subjects in the treatment group (N) under the specified population will be displayed in the header of summary tables.

Data will be summarized using descriptive statistics for continuous variables. Unless otherwise specified, descriptive statistics will include number of subjects, mean, standard deviation, minimum, median, and maximum. Number of subjects with missing values will also be displayed, but only if non-zero. The minimum and maximum statistics will be presented to the same number of decimal places as the original data. The mean and median will be presented to one more decimal place than the original data. The standard deviation will be presented to two more decimal places than the original data.

In summary tables of categorical variables, counts and percentages will be displayed. The count [n] indicates the actual number of subjects in a particular category, which should always be less than or equal to the total number of subjects in the respective study group with known (non-missing) category [M]. Percentage will be obtained by:  $\% = n/M*100$ . Unless otherwise specified, all percentages will be expressed to one decimal place.

All statistical tests will be two-sided at a significance level of  $\alpha = 0.05$ , unless otherwise indicated.

Baselines will be defined separately for Part I and Part II.

- Part I Baseline is defined as the last assessment, scheduled or not, prior to the first dose of the study drug of the study drug in Part I, unless otherwise specified.

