## **6.8.2 Analysis of the primary and key secondary endpoints**

### **6.8.2.1 Primary analysis**

The primary analysis will be performed on the ITT population.

For both primary and key secondary endpoint the number and percentage of subjects achieving the endpoint will be provided based on the subjects with observed endpoint or with intercurrent events (imputed as non-responders), i.e. excluding the subjects who are “missing at random”.

The comparisons between each active group and the placebo group will be performed pairwise. Each comparison will be done using Cochran-Mantel-Haenszel (CMH) test stratified by gender and prior biologic therapy (Yes/No). If all strata have no subjects in one of the treatment groups, a value of 0.1 will be added to all cells in the corresponding table in order to prevent dividing by 0, as suggested in Greenland and Robins (1985). The Breslow-Day test with Tarone’s adjustment for homogeneity of strata will also be performed.

This analysis will be performed on each multiple-imputed set of records and then the results will be pooled as described below.

The estimates of Mantel-Haenszel common risk (response rate) difference between each active dose group and placebo, along with 95% confidence interval, will be pooled assuming the difference is approximately normally distributed, using Rubin’s rule as described in Ratitch, Lipkovich and O’Kelley (2013).

The CMH test statistics as well as the Breslow-Day test statistic will be pooled using the Wilson-Hilferty transformation method from Ratitch, Lipkovich and O’Kelley (2013) and the pooled p-value will be provided.

If the pooled p-value of the Breslow-Day test is  $\geq 0.05$ , the treatment-by-strata interaction is not significant. In the case of heterogeneity between the strata, in-depth analysis will be conducted to understand the source of the interaction; CMH test without stratification will be used then instead of the stratified CMH test.

See sections 11.4.3, 11.4.4, 11.4.5 and 11.4.6 for sample SAS code.

Tests for superiority over placebo for the primary and the key secondary endpoint will be following the step-down approach as described in section 6.1.2.

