### 6.8.2.3 Supplementary analyses

The following supplementary analyses will be performed:

1. Analysis similar to the primary analysis, but on the Per Protocol population using observed cases only with no imputations.
2. The primary and key secondary endpoint will be analyzed using generalized linear mixed model for repeated measures with fixed effects for treatment, visit (time

variable), treatment by visit interaction, gender and prior biologic therapy (yes/no). Visits 7, 8, 9 and 10 will be used. Visit is random effect within Subject with covariance structure. The model will be used to estimate the probability of response (expressed as percentage) at each visit with its 95% confidence interval. Odds ratio for response at Visit 10 (Week 16) for each active treatment vs. placebo with its 95% confidence interval will also be presented with the p-value for the hypothesis of no difference. See section 11.4.7 for details and sample SAS code.

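### PASI50/90/100, PGIC improvement and DLQI 0/1 get only per-arm percentages, so Part I gives no dose-versus-placebo estimate with a confidence interval for them

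*SAP*

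**What the plan says.** SAP 6.8.3.2 lists the binary endpoints (PASI50/75/90/100, IGA response, PGIC improvement, DLQI 0/1, the itch scales and the scalp, nail, joint and palmoplantar responses). It then gives one method for all of them: "Number and percentage of subjects achieving these endpoints will be presented by treatment group along with 95% confidence interval for percentages based on binomial proportion".

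Contrasts with placebo appear in three other places:

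- SAP 6.8.2.1, for the primary and key secondary endpoints: "The estimates of Mantel-Haenszel common risk (response rate) difference between each active dose group and placebo, along with 95% confidence interval, will be pooled". The accompanying CMH test is stratified by gender and prior biologic therapy.
- SAP 6.8.2.3, for the same two endpoints: "The primary and key secondary endpoint will be analyzed using generalized linear mixed model for repeated measures". The odds ratio against placebo is for Week 16.
- SAP 6.8.3.1, for change in PASI score: an MMRM with LS mean differences from placebo at Week 16.

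Protocol 9.8 likewise assigns the CMH test to the primary and key secondary variables and MMRM to continuous secondary endpoints. Its visible text names no method for other binary endpoints. SAP 6.1.2 says p-values for other endpoints are nominal if they are calculated at all. SAP 6.1.3 says those endpoints are summarised as collected, without imputation or special handling of intercurrent events.

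**The concern.** SAP 2.3 sets secondary objectives of evaluating efficacy by the proportion reaching predefined PASI improvement, and of assessing the effect on DLQI and PGIC. An effect is a difference from control. Protocol 9.1.4 includes the placebo arm to show that the products are active, and until Week 16 the arms are randomised and stratified. A one-sample interval per arm uses neither the control nor the strata.

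The plan is also uneven. Change in PASI score gets a supportive contrast with an interval, while PASI50/90/100, cut from the same scores, get none. In a Phase IIb dose-ranging trial, a reader will want to know how far each dose differs from placebo on these endpoints and how precisely. As written, the reader gets two percentages and two intervals that do not answer that question. If someone later calculates a nominal p-value, as 6.1.2 permits, no visible text says which method applies.

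**Working it through.** The plan states no figure on this point, and the sample-size rationale is not in the public text, so there is nothing to reproduce. The check has two parts.

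**1. Which secondary binary endpoints have a contrast at Week 16**

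- PASI75 and IGA response: yes (6.8.2.1 and 6.8.2.3).
- PASI50, PASI90, PASI100: no. Protocol 9.8 lists them as other secondary, with Week 16 included.
- PGIC improvement: no. Protocol 9.8 lists it as other secondary, with Week 16 included.
- DLQI 0/1: no. The SAP added it as other secondary (4.3 and 8). Its list of weeks is partly blacked out, but Protocol 6.1.1 collects DLQI at Week 16.

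**2. What is lost by printing only per-arm intervals**

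Arm size comes from Protocol 4.1: "Approximately 240 subjects will be enrolled in the study in a 1:1:1:1 ratio to the following treatment groups". That is 240/4 = 60 per arm. The documents give no response rates, so all rates below are assumptions.

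*Example A: placebo 3/60 (5%), dose 12/60 (20%).*

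- Exact (Clopper-Pearson) per-arm 95% CIs: 1.0 to 13.9% and 10.8 to 32.3%. They overlap.
- Difference: 20 − 5 = 15 points.
- SE = √(0.05 × 0.95/60 + 0.20 × 0.80/60) = √(0.000792 + 0.002667) = 0.0588.
- Wald 95% CI: 15 ± 1.96 × 5.88 = 15 ± 11.5, or 3.5 to 26.5. The Newcombe interval is 3.1 to 27.2. Both exclude 0.

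*Example B: placebo 6/60 (10%), dose 15/60 (25%).*

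- Exact per-arm 95% CIs: 3.8 to 20.5% and 14.7 to 37.9%. They overlap.
- Difference: 15 points, Newcombe 95% CI 1.3 to 28.3. It excludes 0.

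*Where each reading first shows a difference.* With 6/60 on placebo, the Newcombe CI excludes 0 from 15/60, but the exact per-arm CIs separate only from 20/60. With 12/60 on placebo, the thresholds are 22/60 and 28/60.

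*Over a range of assumed true rates, 60 per arm, two-sided 0.05:*

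| Placebo vs dose | Power of the difference test | Probability that exact per-arm CIs separate | Half-width of the difference CI (points) |
|---|---|---|---|
| 5% vs 20% | 0.71 | 0.30 | 11.5 |
| 10% vs 30% | 0.79 | 0.41 | 13.9 |
| 20% vs 40% | 0.67 | 0.29 | 16.0 |
| 30% vs 50% | 0.61 | 0.25 | 17.2 |

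These figures are unstratified, because the documents give no rates by stratum.

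*Interval type.* Section 6.8.3.2 does not name the binomial interval. At 0/60 a Wald interval has zero width, whereas the exact interval is 0 to 6.0%.

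**The case against.** The strongest reply is that this is a deliberate choice. Confirmatory testing is reserved for PASI75 and IGA response at Week 16. SAP 6.1.2 says that no inferences will be drawn from p-values for other endpoints, and the protocol endpoints are worded as rates. A per-arm rate with an interval reports such an endpoint as worded and breaks no visible commitment. Counts are printed, so a reader can work out a crude difference and its interval. This stands in part: the point is an improvement, not the repair of an error. A crude calculation, however, is neither stratified nor pre-specified.

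Four stronger readings are tempting, and the documents do not support them:

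- *That dose choice would rest on uncontrasted rates.* Each dose is compared with placebo on PASI75 and IGA response (6.8.2.1 and 6.8.2.3) and on change in PASI score (6.8.3.1).
- *That every binary endpoint needs the contrast.* The itch endpoints are exploratory. Protocol 9.1.5 expects only a limited proportion of subjects to qualify for the scalp, nail, joint and palmoplantar assessments, which is too few for stratified contrasts.
- *That overlapping intervals will be misread as no difference.* That predicts reader error; nothing in the SAP tells readers to compare intervals in this way.
- *That a zero-responder arm will show a zero-width interval.* This would follow only from Wald limits, and the SAP does not say which limits it uses.

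Parts of SAP 6.1.2 and Protocol 9.8 are blacked out, and the table shells are a separate document. A contrast specified there cannot be excluded, although the analysis sentence in 6.8.3.2 reads as complete.

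**Conclusion.** The point holds for five other secondary endpoints at Week 16: PASI50, PASI90, PASI100, PGIC improvement and DLQI 0/1. On the visible text, the placebo-controlled part of the trial produces no dose-versus-placebo estimate with an interval for any of them.

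Under the assumed rates, a difference test would detect the effect with probability 0.61 to 0.79, while the per-arm intervals would separate with probability only 0.25 to 0.41. The size of that gap rests on about 60 per arm, on response rates that the documents do not give, and on exact per-arm limits. The primary and key secondary analyses, the step-down procedure and the Type I error rate are unaffected.

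**What to change.** In SAP 6.8.3.2, for PASI50, PASI90, PASI100, PGIC improvement and DLQI 0/1 at Week 16:

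1. Add the Mantel-Haenszel risk difference of each dose against placebo, stratified by gender and prior biologic therapy, with a nominal 95% CI. Label it supportive and outside the step-down.
2. State the missing-data rule for these contrasts. The 6.8.2.1 method runs on multiply imputed data with intercurrent events set to non-response, whereas 6.1.3 leaves these endpoints unimputed, so the method cannot be carried over without one. One option is to count intercurrent events and missing values as non-response, in line with the non-responder imputation in the protocol synopsis.
3. Name Wilson or exact limits for the per-arm intervals.

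Keep the exploratory itch endpoints, the small-subset tertiary endpoints and Parts II to IV descriptive.

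The cost is 5 endpoints × 3 doses = 15 nominal estimates, using the existing Mantel-Haenszel method, plus one added missing-data rule. The extra estimates must not be read as confirmatory, which 6.1.2 already guards against.
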